10.2.1. Serious Adverse Events

A serious adverse event (SAE) is defined as an AE that meets **any** of the following criteria:

- Results in death;
- Is life-threatening- Note: The term “life-threatening” in the definition of “serious” refers to an event in which the patient was at risk of death at the time of the event. It does not refer to an event, which hypothetically might have caused death, if it were more severe.
- Requires hospitalization or prolongation of existing hospitalization- Note: In general, hospitalization for treatment of a pre-existing condition(s) that did not worsen from baseline is not considered an AE(s) and should not be reported as a SAE(s).
- Results in disability/incapacity;
- Is a congenital anomaly/birth defect;
- Is an important medical event- Note: Important medical events that may not result in death, be life threatening, or require hospitalization may be considered an SAE when, based upon appropriate medical judgment, they may jeopardize the patient and may require medical or surgical intervention to prevent one of the outcomes listed above. Examples of such medical events include allergic bronchospasm requiring intensive treatment in an emergency room or at home, blood dyscrasias or convulsions that do not result in inpatient hospitalizations, or the development of drug dependency.

By design of this study SAEs that are endpoint events will only be recorded for the endpoint determination and not captured as SAEs. The intention is that the endpoint events are not reported to IRBs as SAEs, unless the IRB requires that these are reported. Investigators should specifically inform their institution/IRB of this plan and confirm whether or not they want the endpoint events reported. By agreement with the US FDA, these endpoints will also not be reported to the US FDA as SAEs; rather they will be reported as endpoint events. Following adjudication if the event is determined to not meet the criteria for an event, the event will be evaluated as an SAE beginning with that day as Day 0.

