- Composite of CV death, nonfatal MI (including silent MI), non-elective coronary revascularizations (defined as emergent or urgent classifications), or unstable angina determined to be caused by myocardial ischemia by invasive/non-invasive testing and requiring emergent hospitalization;
- Composite of CV death, nonfatal MI (including silent MI), non-elective coronary revascularizations (defined as emergent or urgent classifications), unstable angina determined to be caused by myocardial ischemia by invasive/non-invasive testing and requiring emergent hospitalization, nonfatal stroke, or PVD requiring intervention, such as angioplasty, bypass surgery, or aneurism repair;
- Composite of CV death, nonfatal MI (including silent MI), non-elective coronary revascularizations (defined as emergent or urgent classifications), unstable angina determined to be caused by myocardial ischemia by invasive/non-invasive testing and requiring emergent hospitalization, PVD requiring intervention, or cardiac arrhythmia requiring hospitalization of ≥ 24 hours;
- New CHF;
- New CHF as the primary cause of hospitalization;
- Transient ischemic attack (TIA);
- Amputation for PVD;
- Carotid revascularization;
- All coronary revascularizations defined as the composite of emergent, urgent, elective, or salvage;
- Emergent coronary revascularizations;
- Urgent coronary revascularizations;
- Elective coronary revascularizations;
- Salvage coronary revascularizations;
- Cardiac arrhythmias requiring hospitalization of ≥ 24 hours;

- Cardiac arrest;
- Ischemic stroke;
- Hemorrhagic stroke;
- Fatal or nonfatal stroke in the subset of patients with a history of stroke prior to baseline;
- New onset diabetes, defined as Type 2 diabetes newly diagnosed during the treatment/follow-up period;
- New onset hypertension, defined as blood pressure ≥ 140 mmHg systolic OR ≥ 90 mmHg diastolic newly diagnosed during the treatment/follow-up period;
- Fasting TG, TC, LDL-C, HDL-C, non-HDL-C, VLDL-C, apo B, hs-CRP (hsCRP and $\log[\text{hsCRP}]$), hsTnT, and RLP-C (to be estimated from standard lipid panel, $\text{RLP-C} = \text{TC} - \text{HDL-C} - \text{LDL-C}$ [Varbo 2014]) (based on ITT estimands):
 - Assessment of the relationship between baseline biomarker values and treatment effects within the primary and key secondary composite endpoints,

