4.8.1 Adverse Events

AEs are recorded from the time the informed consent is signed until study participation is complete. Adverse events with onset on or after the date of dispensing study drug for each patient will be considered treatment-emergent (TEAEs). This will include any AE with onset prior to initiation of study drug and increased severity after the treatment initiation.

By design of this study, serious AEs (SAEs) that are endpoint events will only be recorded for the endpoint determination and not captured as SAEs. Following adjudication, if the event is determined to not meet the criteria for an event, the event will be evaluated as an SAE.

Adverse events will be coded using the most recent available Medical Dictionary for Regulatory Activities (MedDRA) Version. Coding includes system organ class (SOC) and preferred term (PT). All AEs will be listed by patient and by SOC and PT; these listings will present detailed information concerning adverse events, including the verbatim description, time of onset and resolution, severity, relationship to study drug, action taken, and outcome.

Pre-treatment AEs:

Pre-treatment-emergent AEs will be defined as any AE that started before the patient's randomization. (An AE that was ongoing at the time of randomization and subsequently increased in severity is also considered treatment-emergent.) Pre-treatment AEs will be listed separately from TEAEs.

Treatment-emergent AEs:

For each patient, the following AEs will be defined as TEAEs:

- AEs occurring after randomization;
- AEs occurring within 30 days after the completion or withdrawal from study;
- AEs started prior to randomization but worsened in severity following randomization;
- AEs with partial onset dates if the AE stop date is after randomization and the dates do not definitively place the AE start date before randomization; and
- AEs with completely missing onset dates.

The frequency and percentage of patients with any TEAEs will be summarized. TEAEs will be presented by SOC and PT. At each summary level, a patient will be counted only once for each TEAE he/she experiences within that level, regardless of how many occurrences of that TEAE that patient experienced. The percentage of patients having had at least one TEAE at each level will be calculated.

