3. ADDITIONAL EXPLORATORY EFFICACY ANALYSES

The following list presents additional pre-specified exploratory efficacy analyses that could be of interest to the general clinical and scientific community:

- Non-fatal myocardial infarction (MI) (including both clinical manifestation and silent MI categorizations) – intent-to-treat (ITT) Population
- Evaluation of effect of time-weighted (or area under the curve [AUC]) eicosapentaenoic acid (EPA) data on the primary and key secondary composite endpoints – ITT Population
- Sensitivity analyses on the primary and key secondary composite endpoints by excluding elective coronary artery revascularizations if onset is <3 months post randomization; and also excluding peri-procedural MIs – ITT Population
- Two silent MI (SMI) sensitivity analyses on the primary and key secondary composite endpoints – ITT Population:
 - counting all potential SMIs identified by Clinical Endpoint Committee (CEC) electrocardiogram (ECG) reviewer, whether confirmed at final ECG or not; and,
 - counting only potential SMIs that have at least one confirmatory ECG showing persistence of Q-waves (even if not present at final ECG)
- Non-alcoholic fatty liver disease (NAFLD) analyses using NAFLD Fibrosis Score (NFS), assessing – ITT Population:
 - effect on primary and key secondary composite endpoints by baseline NFS category; and,
 - treatment effect on change from baseline in NFS at 1 and 5 years
- Individual and combined on-treatment goal achievement of triglyceride (TG) ≤ 150 mg/dL and hsCRP ≤ 2 mg/L at 2 years, and end of study – ITT Population
- Additional renal function (eGFR) analyses – ITT Population:
 - primary and key secondary composite endpoints for patients with baseline renal dysfunction [eGFR] ≥ 60 and < 90 mL/min/1.73m²

- treatment effect on change from baseline in renal function (eGFR) at 1 and 5 years
- Sensitivity analyses on the primary and key secondary composite endpoints by excluding patients with post-randomization low density lipoprotein cholesterol (LDL-C) values >100 mg/dL; and another for >70 mg/dL – ITT Population
- Analyses of hospitalization data (pooled positively adjudicated unstable angina requiring hospitalization, congestive heart failure [CHF] requiring hospitalization, and cardiac arrhythmia requiring hospitalization) – ITT Population
 - Time from randomization to first hospitalization
 - Recurrent event analysis on hospitalization

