- Using archived frozen biosamples (serum and whole blood); potential analyses of treatment effects on biomarkers and genetic markers and associations with outcomes, including but not limited to the following:
 - Low density lipoprotein particle number (LDL-P)
 - Remnant lipoprotein cholesterol (RLP-C) (measured)
 - Low density lipoprotein triglyceride (LDL-TG)
 - Oxidized low density lipoprotein (Ox-LDL)
 - Galectin-3
 - Lipoprotein a (Lp(a)) at baseline, as a predictor of CVD benefit
 - Lipoprotein-associated phospholipase-A2 (LpPLA2)
 - High density lipoprotein subfraction 2 (HDL2), high density lipoprotein subfraction 3 (HDL3), apolipoprotein A-I (apo A-I), apolipoprotein A-II (apo A-II), high density lipoprotein particle number (HDL-P), apolipoprotein C-III (apo C-III) (and apo C-III in apo-B containing proteins), apolipoprotein A-V (apo A-V), apolipoprotein E (Apo E) subtypes (2, 3, 4), interleukin 6 (IL-6), lipoprotein lipase (LPL)
 - Analyses may include change (and percent change) from baseline, and on-treatment comparisons between treatment groups with testing as predictors of CV risk
- Exploratory analyses of differential treatment effects for potential benefit (from adverse event reports) of:
 - ophthalmologic changes (e.g., incidence of age-related macular degeneration, progression of diabetic retinopathy)

- cognitive impairment (Schwarz 2018)
- erectile dysfunction (Shim 2016)
- ischemic cardiomyopathy (as indicated by hospitalization for CHF, implantable cardioverter defibrillator [ICD] placement etc.)
- Additional genetic bioassays not included in the REDUCE-IT SAP including genes which may relate to triglyceride, lipid metabolism, and CVD
- Effects of potential mediators identified *post hoc* on primary/key secondary outcome measures (Inzucchi 2018)

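### The ischemic-cardiomyopathy item in the list of additional analyses reads CHF hospitalizations from adverse event reports, where the recording rules leave out CEC-confirmed endpoint admissions

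*Combined protocol and SAP*

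**What the plan says.** PLAA section 3 introduces a group of four items as "Exploratory analyses of differential treatment effects for potential benefit (from adverse event reports) of" the conditions that follow. They are eye changes, cognitive impairment, erectile dysfunction and "ischemic cardiomyopathy (as indicated by hospitalization for CHF, implantable cardioverter defibrillator [ICD] placement etc". The source named in the introduction governs all four.

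The SAP lists "New CHF as the primary cause of hospitalization" among the tertiary time-to-event endpoints (section 4.7.4; also Protocol 9.2.3). Protocol 5.3 gives the CEC the blinded validation of primary, secondary and tertiary outcome events alike.

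Protocol 10.2.1 makes an event serious when, among other criteria, it "Requires hospitalization or prolongation of existing hospitalization". The same section states: "By design of this study SAEs that are endpoint events will only be recorded for the endpoint determination and not captured as SAEs". SAP 4.8.1 repeats the rule and adds that, after adjudication, "if the event is determined to not meet the criteria for an event, the event will be evaluated as an SAE".

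Another item in PLAA section 3 analyses hospitalizations from a different source: "pooled positively adjudicated unstable angina requiring hospitalization, congestive heart failure [CHF] requiring hospitalization", together with arrhythmia admissions.

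**The concern.** AE reports are a natural source for the eye, cognition and erectile-dysfunction items, which are not adjudicated endpoints. The first-named indicator of ischemic cardiomyopathy is different, because hospitalization for new CHF goes to the CEC. The recording rules then sort these admissions in the wrong direction for this item: a confirmed one stays in the endpoint record, and a rejected one goes back toward the SAE data.

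At stake is the meaning of one exploratory result. A difference, or the lack of one, could be reported as the effect on ischemic cardiomyopathy although its CHF part rests on a selected subset of admissions. The same list would also contain two analyses of CHF hospitalization drawn from different sources, with nothing to tell the reader so.

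**Working it through.** There is no planned figure to reproduce. The check follows a CHF admission through the recording rules.

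1. The investigator reports the admission. As a hospitalization it is serious (Protocol 10.2.1), so it does not enter as a non-serious AE.
2. If it is a suspected new-CHF hospitalization, it goes to the CEC (Protocol 5.3 and 9.2.3).
3. If confirmed, it is kept for the endpoint and not captured as an SAE. If rejected, it is evaluated as an SAE (Protocol 10.2.1, SAP 4.8.1).
4. The cardiomyopathy item then reads the AE reports (PLAA section 3).

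Later in SAP 4.8.1, the planned output includes a summary category and tables for treatment-emergent events adjudicated as events. It also includes a listing that shows whether each event was confirmed or ruled out. That presupposes that confirmed events are in the AE data, which conflicts with step 3. Both readings, beside the other PLAA item:

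| Type of CHF admission | AE source, non-capture rule followed | AE source, if the later SAP 4.8.1 tables reflect capture | PLAA pooled hospitalization item |
|---|---|---|---|
| Confirmed by the CEC as an endpoint | absent | present | present |
| Submitted and rejected by the CEC | present | present | absent |
| Not an endpoint event (for example known heart failure, if not counted as new CHF) | present if reported as an AE | present if reported as an AE | absent |

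On the first reading, the two PLAA items share no submitted CHF admission. On the second, the cardiomyopathy item contains the confirmed set plus the others, unfiltered.

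For size on the first reading, let c be the share of submitted CHF admissions that the CEC confirms. The share left in the AE source is 1 − c, and all of those were rejected. The documents give no value for c, so these are assumptions:

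- c = 50%: 1 − 0.50 = 50% left
- c = 70%: 1 − 0.70 = 30% left
- c = 90%: 1 − 0.90 = 10% left

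In each case none of the confirmed admissions is left. The formula covers submitted admissions only, not the last row of the table.

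**The case against.** The strongest objection is the later text of SAP 4.8.1. It expects AE outputs to hold confirmed and ruled-out events, with a flag in the listing, so it cannot be taken as certain that confirmed admissions are missing. This stands as a limit on the claim. It does not rescue the item, which states no filter and would then pool confirmed with rejected admissions.

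A reader might infer that the item counts only admissions that are not heart failure, so that its expected hazard ratio is 1.0 whatever the drug does. The documents do not support this. Appendix B 23.8 requires all five criteria: a primary heart-failure diagnosis, a stay of at least 24 hours, symptoms, objective evidence and intensified treatment. A genuine heart-failure admission can fail on length of stay or on documentation.

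Nor is everything left in the AE source necessarily a rejected event. The endpoint is new CHF, only NYHA class IV heart failure is excluded at entry (Protocol 4.2), and worsening of a baseline condition is a reportable AE (Protocol 10.2). Appendix B 23.8 covers both new and worsening heart failure, so it is unclear whether admissions for known heart failure count as endpoint events. Some may reach the AE reports.

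ICD placement is not a listed endpoint, so that indicator is largely untouched, and the item leaves room for others. A claim that the whole analysis could detect neither benefit nor harm would go too far.

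Finally, confirmed CHF is analysed elsewhere: as a tertiary endpoint, in two composites in SAP Addendum section 6, and in other PLAA items. The PLAA introduction says that its analyses may be left undone or unreported. These facts limit the consequence; they do not make the named source suitable.

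**Conclusion.** The concern holds for the CHF hospitalization component of this one item. Under the non-capture rule, that component omits CEC-confirmed endpoint admissions and keeps rejected ones, plus any heart-failure admissions that are not endpoint events. Under the conflicting tables in SAP 4.8.1, it mixes confirmed and rejected admissions. On either reading it could misstate the treatment effect, and it is inconsistent with the PLAA item that uses confirmed CHF hospitalizations.

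The direction and size of any distortion cannot be derived from the documents. The range of 50% down to 10% of submitted admissions left in the source rests on the assumed confirmation rates and on the first reading. Severity is minor: the analysis is optional, exploratory and outside the testing scheme, and no confirmatory conclusion is affected.

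**What to change.** In PLAA section 3, state that CHF hospitalizations for the ischemic-cardiomyopathy item come from the CEC-confirmed events, as in the pooled hospitalization item. Keep AE reports for indicators that are not adjudicated, such as ICD placement, and for the eye, cognition and erectile-dysfunction items.

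In SAP 4.8.1, reconcile the rule that endpoint events are not captured as SAEs with the planned tables and listing of events adjudicated as endpoints, and say which events the AE data will hold.

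The cost is one line in the PLAA and a short clarification in the SAP, both to be made before database lock and unblinding. The adjudicated CHF data are already required for the tertiary endpoint, so the CHF part needs no new collection.

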4. ADDITIONAL EXPLORATORY SAFETY ANALYSES

The following list presents additional pre-specified exploratory safety analyses that could be of interest to the general clinical and scientific community:

- Number and percent of patients with the following liver function abnormalities – Safety Population:
 - Alanine aminotransferase (ALT) ≥ 3 x Upper Limit of Normal (ULN) + Total Bilirubin > 1.5 x ULN
 - ALT ≥ 5 x ULN
 - ALT ≥ 3 x ULN with an appearance of rash or worsening hepatitis symptoms
- Number and percent of patients with treatment-emergent cancer (overall, Lung Cancer, and Prostate Cancer) reported as adverse event (AE); each in 2 populations (ITT and hsCRP ≥ 2 mg/L) – Safety Population
- Number and percent of patients with treatment-emergent depression and social dysfunction reported as AE – Safety Population

